### **7.1.3 Safety Population**

All randomized subjects who received at least one study treatment application. Unless otherwise stated, the safety population will be the default analysis population for all safety and tolerability analyses. Analyses will be performed based on actual treatment received, even if different from treatment group to which subjects were randomized.

## **7.2 Derived Data**

This section describes the derivations required for statistical analysis. Unless otherwise stated, variables derived in the source data will not be re-calculated.

### **7.2.1 Baseline**

For endpoints that are based on assessments that are collected once per visit, baseline is defined as the last non-missing value (either scheduled, unscheduled or repeat) before the subject receives the first dose of study drug.

For baseline of Counter regulatory hormone parameters see Section [7.2.9](#).

For baseline of CGM derived endpoints see Section [7.2.10](#).

For baseline of hypoglycemia symptom questionnaire parameters see Section [7.2.11](#).

### **7.2.2 Duration/Study Day/Time**

Study day will be calculated as the number of days from first dose of study drug.

- date of event – date of first dose of study drug + 1, for events on or after day of first dose;
- date of event – date of first dose of study drug, for events before day of first dose.

### **7.2.3 Conventions for Missing and Partial Dates**

All rules explained below for partial/missing dates will be followed unless contradicted by any other data recorded on the electronic Case Report Form (eCRF).

All dates presented in the individual subject listings will be presented as recorded on the eCRF (i.e., not completed as per the below rules).

### **7.2.4 Missing/Partial Start/Stop Date of Adverse Events and Concomitant Medications**

When the AE start date is incomplete, then it will be imputed for analysis purposes (e.g. when defining whether AE is treatment-emergent or not).

For concomitant medications, incomplete or missing start date and stop date will be imputed for analysis purposes (e.g. prior and concomitant medications). When the start date and the stop date are both incomplete for a subject, consider imputing the start date first.

Start and stop dates will be imputed as follows:

#### **Incomplete Start Date**

##### **Missing day and month**

- If the year of the incomplete start date is the same as the year of the date of the first dose of investigational product, then the day and month of the date of the first dose will be assigned to the missing fields.
- If the year of the incomplete start date is before the year of the date of the first dose of investigational product, then December 31 will be assigned to the missing fields.
- If the year of the incomplete start date is after the year of the date of the first dose of investigational product, then January 1 will be assigned to the missing fields.

##### **Missing month only**

- The day will be treated as missing and both month and day will be replaced according to the above procedure.

##### **Missing day only**

- If the month and year of the incomplete start date are the same as the month and year of the date of the first dose of investigational product, then the day of the first dose will be assigned to the missing day.
- If either the year is before the year of the date of the first dose of investigational product or if both years are the same but the month is before the month of the date of the first dose of investigational product, then the last day of the month will be assigned to the missing day.
- If either the year is after the year of the date of the first dose of investigational product or if both years are the same but the month is after the month of the date of the first dose of investigational product, then the first day of the month will be assigned to the missing day.

#### **Missing start date**

If the stop date is after the date of the first dose of investigational product, the date of the first dose of investigational product will be assigned to the missing start date

If the stop date is before the date of the first dose of investigational product, the stop date will be assigned to the missing start date.

#### **Incomplete Stop Date**

##### **Missing day and month**

- If the year of the incomplete stop date is the same as the year of the date of the last dose of investigational product, then the day and month of the date of the last dose will be assigned to the missing fields.
- If the year of the incomplete stop date is before the year of the date of the last dose of investigational product, then December 31 will be assigned to the missing fields.
- If the year of the incomplete stop date is after the year of the date of the last dose of investigational product, then January 1 will be assigned to the missing fields.

##### **Missing month only**

- The day will be treated as missing and both month and day will be replaced according to the above procedure.

##### **Missing day only**

- If the month and year of the incomplete stop date are the same as the month and year of the date of the last dose of investigational product, then the day of the last dose will be assigned to the missing day.
- If either the year is before the year of the date of the last dose of investigational product or if both years are the same but the month is before the month of the date of the last dose of investigational product, then the last day of the month will be assigned to the missing day.
- If either the year is after the year of the date of the last dose of investigational product or if both years are the same but the month is after the month of the date of the last dose of investigational product, then the first day of the month will be assigned to the missing day.

### **7.2.5 Missing Diagnosis Dates**

If the month and year are present but the day is missing, then diagnosis day will be set to "01". If only year is recorded, then diagnosis date and month will be set as "01-Jan" for that year.

### **7.2.6 Duration of Study Drug Exposure**

Duration of study drug exposure will be calculated as date of last dosing minus the date of first dosing + 1. The exposure duration will not consider breaks in therapy.

### **7.2.7 Inexact Values**

If a reported value of a clinical laboratory parameter cannot be used in a statistical summary table due, for example, to the fact that a character string is reported for a parameter of the numerical type, a coded value needs to be appropriately determined and used in the statistical analyses. Value of  $X+0.0001$  will be used to impute ">X" character value and  $X-0.0001$  will be used to impute "<X". That is, if X equal to 60,  $60.0001$  will be used to impute character value of ">60" and  $59.999$  will be used to impute "<60".

In the case where a laboratory value is recorded as " $\geq X$ " or " $\leq X$ ", a value of X will be taken for analysis purposes.

However, the reported values will be presented in data listings.

### **7.2.8 Unscheduled Visits and Repeated assessments**

Only scheduled post-baseline safety and tolerability values will be tabulated. If more than one value is available at scheduled visit, then the last one will be used for analysis.

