### **9.6. Subject Withdrawal**

Subjects may withdraw from the study at any time at their own request, or they may be withdrawn at any time at the discretion of the investigator or Sponsor for safety, behavioral or administrative reasons. If a subject does not return for a scheduled visit, every effort should be made to contact the subject to determine the reason(s) why the subject failed to return for the scheduled visit, and to reschedule the missed visit. In all circumstances, every effort should be made to document subject outcome. Information regarding the reason for not completing the study will be recorded in the CRF. The investigator should inquire about the reason for withdrawal, request that the subject return for a final visit, and follow-up with the subject

regarding any unresolved AEs. It will be documented whether each subject completed the study. Any subject who receives at least one treatment dose of study medication will be included in the safety analysis.

If a decision by the investigator or sponsor is made to withdraw a subject, a final visit should be scheduled soon after the decision to withdraw is made. The subject will be asked to return to site for the assessments listed in Section 9.5.11.

If the subject withdraws from the study and also withdraws consent, no further evaluations should be performed, and no additional data should be collected. The Sponsor may retain and continue to use any data collected before such withdrawal of consent

Approved

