### **10.17. Subject Monitoring**

Subjects will be monitored for AEs throughout the study by the study staff. The principal investigator or designated sub-investigator will be on site for drug administration initiation and during hypoglycemia induction procedures. If necessary, a physician, either at the study site or in a nearby hospital, will administer treatment for any AEs.

Safety parameters, including laboratory results and ECGs, will be assessed by the principal investigator or his/her delegate using the site's criteria for clinical laboratory and ECG acceptance ranges as suggested guidelines in making the medical assessment.

Scheduled safety measurements will be repeated according to appropriate SOPs or upon request from a physician. Any abnormal repeated measurement will be evaluated by a physician and repeated if judged necessary. Further action may be taken on the physician's request.

Subjects will be advised to notify their health care professionals (e.g., physician, dentist, and/or pharmacist) that they are participating in a clinical research study of a drug called synthetic Glucagon Injection before taking any medicines or undergoing any medical procedure.

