### **7.3.2 Summary statistics**

Data will be tabulated by time point where appropriate. The total number of subjects in the study group (N) under the stated population will be displayed in the header of summary tables and figures.

All summaries will be presented by treatment group for baseline and each scheduled visit and timepoint, where applicable. If more than one assessment available per timepoint, then last assessment will be used for analysis.

Summaries will be presented by treatment group and overall. Treatment group labels will be displayed as follows:

CSGI			Placebo	Total
Low Dose (20 ug/hr)	High Dose (80 ug/hr)	Combined (Low + High)		

Listings will be sorted in the following order: subject, parameter, and visit unless otherwise stated. All data will be listed, subjects who were not randomized will be displayed after the randomized treatment/sequence groups.

Continuous variables will be summarized by the number of non-missing observations, mean, median, standard deviation, and minimum and maximum.

Categorical variables will be summarized with frequencies and percentages. For each variable, all pre-specified categories will be shown. Zero counts will be presented without percent.

N will be used as percentage denominator in descriptive summaries, if not specified otherwise.

Missing will be counted as difference of subjects at each visit and number of assessments. Note: Records collected from eCRF or eDT will not be used for 'Missing' statistics and can be used only for reference.

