### **7.11.2 Laboratory Data**

Descriptive statistics of the observed values and change from baseline (continuous data) will be presented by treatment group and visit for each hematology, urinalysis and serum chemistry parameter. Each measurement (continuous data) will be classed as below, within, or above normal range, based on ranges supplied by the laboratory used. Shift tables in relation to the normal range from baseline to each follow-up visit will be presented.

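### Post-baseline safety tables use only scheduled values and keep the last one at a visit, with no worst-value table, so some abnormal values appear only in listings

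*SAP*

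**What the plan says.** The selection rule has two parts, both in SAP 7.2.8: "Only scheduled post-baseline safety and tolerability values will be tabulated. If more than one value is available at scheduled visit, then the last one will" (the sentence goes on to make that last value the one analysed). SAP 7.3.2 applies the second part to timepoints as well: "If more than one assessment available per timepoint, then last assessment will be used for analysis".

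Baseline follows a wider rule. In SAP 7.2.1, "baseline is defined as the last non-missing value (either scheduled, unscheduled or repeat) before the subject receives the first dose of study drug".

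The outputs exposed to the rule are organised by visit. For laboratory data, SAP 7.11.2 says "Shift tables in relation to the normal range from baseline to each follow-up visit will be presented"; SAP 7.11.4 plans the same for the overall ECG interpretation; SAP 7.11.3 plans descriptive statistics by visit for vital signs. The table list in SAP 12 has no worst-value, any-post-baseline or treatment-emergent-abnormality table.

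Protocol 10.17 provides for repeating scheduled safety measurements under SOPs or at a physician's request, and adds: "Any abnormal repeated measurement will be evaluated by a physician and repeated if judged necessary". Protocol 10.4 allows extra blood pressure and heart rate readings for safety.

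For a subject withdrawn by the investigator or sponsor, protocol 9.6 says "a final visit should be scheduled soon after the decision to withdraw is made" and refers to Section 9.5.11 for its content. The SAP gives no visit mapping for that visit.

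**The concern.** Repeat safety measurements are seldom taken at random. When a repeat is ordered because a result looked abnormal, keeping the last value puts the repeat in the table in place of the result that prompted it. When an abnormality is found between visits, the restriction to scheduled values keeps it out altogether. Both mechanisms move the tabulated post-baseline picture toward normal.

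The schedule leaves little redundancy. In protocol Table 6, CBC/CMP falls at Visits 1, 3, 7 and 11. Visit 3 precedes the first dose, so Visit 7 is the only scheduled on-treatment laboratory point. ECG is scheduled at Visits 1 and 7 only, so the ECG shift table rests on one post-baseline value per subject. With 16 subjects per arm, a single replaced or omitted value changes a table cell noticeably. The AE tables are not a full backstop: under protocol 10.5, repeating a test because it was abnormal is not in itself an AE. SAP 9 states that there is no data and safety monitoring board.

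**Working it through.** The plan gives no figure for this rule, so there is nothing to reproduce. The check is a reading of the rule case by case, followed by an illustration under stated assumptions.

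**Step 1. What happens to an abnormal post-baseline value under SAP 7.2.8**

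| Situation | Summary and shift tables | Listings |
|---|---|---|
| Abnormal at a scheduled visit, not repeated | Kept | Kept |
| Abnormal at a scheduled visit, normal repeat filed under the same visit | Replaced by the repeat | Kept |
| Abnormal at a scheduled visit, repeat on a later unscheduled date | Original kept; repeat excluded | Both kept |
| Abnormal only at an unscheduled assessment | Not tabulated | Kept |
| Found at an early-withdrawal visit | Not stated | Kept |

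The listing column rests on SAP 7.3.2, which has all data listed, and on the laboratory, vital-sign and ECG listings in SAP 12. Protocol 10.2 sends blood samples to a central laboratory. I infer that results often return after the visit, so that many laboratory repeats fall in the third row. Same-visit replacement then mainly concerns ECG and vital signs.

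**Step 2. The withdrawal visit**

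Protocol 9.6 points to Section 9.5.11. In the body that section is Visit 10, a CGM placement visit for which Table 6 has no CBC/CMP, vital signs or ECG. In the table of contents, 9.5.11 is Visit 11, which in the body is Section 9.5.12 and has CBC/CMP and vital signs but no ECG. On neither reading is a withdrawal ECG specified.

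**Step 3. Illustration of same-visit replacement**

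Assumptions, none of them in the documents: first value and repeat are bivariate normal with within-subject correlation r; the reference range covers 95%, so 5% of first values are abnormal by chance; a share q of abnormal values is repeated at the same visit; there is no treatment effect. Let p be the probability that the repeat is abnormal given an abnormal first value. Then

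share tabulated as abnormal = 5% × [(1 − q) + q × p].

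| r | p | q = 25% | q = 50% | q = 100% |
|---|---|---|---|---|
| 0.5 | 0.185 | 4.0% | 3.0% | 0.9% |
| 0.7 | 0.331 | 4.2% | 3.3% | 1.7% |
| 0.8 | 0.439 | 4.3% | 3.6% | 2.2% |
| 0.9 | 0.593 | 4.5% | 4.0% | 3.0% |

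Example: r = 0.8, q = 50% gives 5% × (0.5 + 0.5 × 0.439) = 3.6%. Keeping the first value would leave 5.0%.

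**Step 4. The same model with a real shift**

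With an upper limit at the 97.5th percentile and an assumed upward shift of 2 SD, p is 0.755, 0.802 and 0.861 at r = 0.7, 0.8 and 0.9. At 3 SD it is 0.916, 0.931 and 0.951. The larger the true effect, the less the last-value rule hides it.

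**The case against.** The strongest case against is that this is a common by-visit convention and little is lost. Much of that case stands.

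- **Visibility elsewhere.** Every value stays in the listings, protocol 11.3.2 flags out-of-range laboratory values, and AE tables do not use the rule. With 48 subjects the listings can be read subject by subject. This limits the harm, but a listing does not compare arms.
- **Repeats are not stated to follow abnormality in general.** Protocol 10.17 names abnormality only as a ground for repeating an already repeated value. That repeats tend to follow abnormal results is a reasonable inference.
- **Direction.** A reader might infer that the bias always runs toward fewer abnormal shifts. The documents do not support that. The baseline rule also takes the last value, repeats included, so an abnormal baseline repeated to normal can create an apparent shift to abnormal.
- **Size.** A reader might take Step 3 with every abnormality repeated at correlation 0.7 to 0.9, where 41% to 67% of first abnormalities disappear (1 − 0.593 and 1 − 0.331), as the share of signal lost. It is not. That model has no treatment effect, so what disappears is chance excursions, and Step 4 shows that most abnormalities caused by a large shift persist.
- **Withdrawals.** A reader might infer that withdrawal-visit values are dropped, or that an on-treatment ECG is lost. The SAP is silent on the first. Neither reading of Section 9.5.11 specifies an ECG, and a visit held after the decision to withdraw need not be on treatment.
- **Arms.** The rule applies alike to all blinded arms, so nothing suggests that it favours one.

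What none of this removes is the absence of any planned table that would show abnormalities found off schedule or replaced by a same-visit repeat.

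**Conclusion.** The point holds as a gap in the safety tabulations for laboratory, ECG and vital-sign data. Followed as written, the SAP leaves two kinds of abnormal value out of its tables: those seen only at unscheduled assessments, and those followed by a normal repeat within the same scheduled visit. The likely effect is some under-reporting of post-baseline abnormalities in all arms.

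Its size cannot be derived from the documents. They give no repeat frequency, within-subject correlation or count of unscheduled assessments. Under the Step 3 assumptions, same-visit replacement lowers the tabulated share from 5.0% to between 0.9% and 4.5%; this shows direction and range only. Abnormalities found off schedule cannot be sized at all.

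Handling of early-withdrawal values is undefined and at risk of exclusion, and the Section 9.5.11 reference is inconsistent within the protocol. This is a cheap improvement. It does not invalidate the safety analysis.

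**What to change.** 1. In SAP 7.2.8, keep one prespecified value per visit for by-visit summaries. The last-value convention can stay for that purpose.
2. In SAP 7.2.8, 7.11.2 and 7.11.4, add a shift table from baseline to the worst post-baseline value, separately for the on-treatment and follow-up periods. It should use scheduled, repeat, unscheduled and early-termination values, excluding only documented laboratory errors. Add the tables to SAP 12.
3. State in SAP 7.2.8 how early-termination values map to visits.
4. Reconcile the Section 9.5.11 reference in protocol 9.6, so that body and table of contents point to the same visit and the content of the withdrawal visit is clear.

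The cost is SAP wording, a protocol cross-reference correction and programming of a worst-value flag and a few tables. Items 1 to 3 need no new data. The downside is that the added tables will show a few more transient abnormalities, which the by-visit tables and listings beside them will put in context.

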### **7.2.9 Counter Regulatory Hormones**

Hypoglycemia induction is conducted at

- Visit 3 Day 1 (baseline);
- Visit 7 (Week 4);
- Visit 9 (3 Month Follow-Up);
- Visit 11 (6 Month Follow-Up).

During the hypoglycemia induction, blood samples (2) for counter regulatory hormones (growth, cortisol, epinephrine, norepinephrine, glucagon) are drawn 10 minutes apart at the following steps after meeting target PG value for minimum amount of time:

- Baseline Stabilization (BS; defined as having PG between 90-110 mg/dL for at least 60 minutes, target PG value 100 mg/dL).
- Hypoglycemia induction and stabilization, 2nd step (HIS2, Subject has maintained a PG between 45-54 mg/dl for at least 30 minutes, target PG value 50 mg/dL)

The average of the non-missing results at each step will be used in analysis.

Assessments captured during the hypoglycemia induction at Visit 3, Day 1 are baseline values.

Counter regulatory hormone response to the induction is defined as the difference between HIS2 and BS value (e.g., response=HIS2 average value – BS average value).

### 7.2.10 CGM Derived Parameters

CGM readings occur every 5 mins. Hence in a complete 24-hour period, 288 CGM readings would be captured. The following endpoints will be calculated per day (e.g., 24-hour period starting from CSGI injection).

- Proportional time spent with interstitial glucose < 70 mg/dL;
- Proportional time spent with interstitial glucose < 60 mg/dL;
- Proportional time spent with interstitial glucose < 50 mg/dL;
- Proportional time within  $70 \leq \text{interstitial glucose} < 180$  mg/dL;
- Proportional time with interstitial glucose  $\geq 180$  mg/dL.

Proportional time spent with  $IG < X$  mg/dL = (time spent with  $IG < X$  mg/dL (minutes) / total time spent with CGM (minutes)) \* 100 where  $x = 70, 60$  or  $50$ , given the continuous CGM readings.

- Rate of hypoglycemic event episodes at thresholds of plasma glucose <70 mg/dL;
- Rate of hypoglycemic event episodes at thresholds of plasma glucose <60 mg/dL;
- Rate of hypoglycemic event episodes at thresholds of plasma glucose <50 mg/dL;

Rate of hypoglycemic event episodes at thresholds of <X mg/dL is defined as the number of episodes with  $PG < X$  mg/dL, where 70, 60 or 50. Subsequent PG measures with the result of < X mg/dL should be considered as the same episode.

- Average interstitial glucose;
- Interstitial glucose standard deviation;
- Area over the curve (AOC) of the reduction from baseline in the interstitial glucose from T0 (defined as the date/time of the CSGI injection) to Tx, where x corresponds to time when interstitial glucose < 70, <60 and <50 mg/dL is achieved.

AOC calculations will be done using the standard trapezoidal rule

$$AOC = -\left(\sum_{i=0}^x \left(\frac{\text{abs}(\text{reduction in } IG_i) + \text{abs}(\text{reduction in } IG_{i+1})}{2}\right) * (T_{i+1} - T_i)\right)$$

Where:  $\text{abs}(\text{reduction in } IG_i)$  = absolute value of change from baseline in interstitial glucose at time i, and  $(T_{i+1} - T_i)$  is the Time difference in minutes between time i and time i+1.

For endpoints that will be calculated per day - baseline will be based on the CGM data collected on the latest day prior to the date/time of the first CSGI injection. For the AOC endpoint baseline will be the latest interstitial glucose measure obtained prior to the date/time of the first CSGI injection.

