### **9.5.3. Visit 3 (Day 1) Start of Treatment Phase**

The subject will arrive to the clinic at about 6-9 am for the planned randomization. The subject will fast after midnight until the end of the hypoglycemia procedure the subsequent day.

The following procedures will be completed:

1. Eligibility Review
2. The subject's CGM, electronic diary, and insulin utilization data will be collected/uploaded to the electronic data capture (EDC).
3. Assessment will be made whether the CGM baseline data meet the criteria of minimum 6 days are recorded using the CGM device. The clinic will be notified within 30 minutes from time of subject data upload as follows:
  - a. If the data do not meet the above criteria, the subject is inserted with another CGM for renewed baseline of CGM period. The visit is rescheduled for a week later and the subject is sent home with instructions for another baseline attempt. Should the second baseline period not yield eligible CGM data, the subject will stop further participation in the procedures.
  - b. If the data meets criteria, the visit proceeds.

The following procedures will be carried out once CGM data is confirmed. This includes a confirmation that the subject did not have a hypoglycemic event, < 70 mg/dL during the 8 hours prior to the induction.

4. A new CGM sensor will be inserted.
5. The subject will be asked of any changes in concomitant medications since their last visit and this will be documented in the CRF.
6. The subject will fill out the Gold Score about hypoglycemia awareness.
7. Urine pregnancy test for women of childbearing potential.
8. The subject will be reminded to refrain from using his or her own insulin until the hypoglycemia induction procedure the following day is complete. However, the subject will withhold their long acting insulin.

9. The Insulin Diary will be collected from the previous visit and a new diary given to the subject to collect the following, daily:
  - Total daily dose
  - Total Daily Bolus
  - Basal Rate
10. IV lines are inserted in both upper extremities. One side will be used for both IV insulin infusion and IV glucose infusion. The other side will be used for venous sampling during the clamp procedure.
11. Collection of venous blood for the following tests as outlined in the Schedule of Activities:
  - CBC/CMP
  - Plasma glucagon (PK) prior to Omnipod placement

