**7.2.10.1 Weekly endpoints**

Additionally, all derived CGM endpoints will be derived on a weekly basis. The following weeks will be analyzed: Baseline (Week), Week 1, Week 2, Week 3, Week 4, Month 3 and Month 6. CGM-Derived parameters will be based on CGM data that fall in the following timeframe:

Week	Time window (Days)	
Baseline	7 days prior to day 1	
Week 1	1	7
Week 2	8	14
Week 3	15	21
Week 4	22	28
Month 3	7 days prior to date of Month 3 visit	
Month 6	7 days prior to date of Month 6 visit	

When deriving weekly endpoints - baseline will be based on the CGM data collected 7 days prior to the date/time of the first CSGI injection. For the AOC endpoint baseline will be the same as for the AOC calculated by day.

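### The CGM hypoglycemic-episode rate is a count per nominal day or week, not adjusted for the CGM time actually recorded

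*SAP*

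**What the plan says.** SAP 7.2.10 states "CGM readings occur every 5 mins" and, for the CGM parameters, "The following endpoints will be calculated per day". Section 7.2.10.1 adds that "all derived CGM endpoints will be derived on a weekly basis", over fixed windows: the 7 days before Day 1 for baseline and Days 22 to 28 for Week 4.

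Within 7.2.10 two kinds of endpoint are treated differently:

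- Proportional time below 70, 60 or 50 mg/dL is time below the threshold over a divisor worded as "total time spent with CGM (minutes").
- The episode rate at each threshold "is defined as the number of episodes with" PG below X. No divisor follows. The only other rule is "Subsequent PG measures with the result of < X mg/dL should be considered as the same episode".

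The one recording criterion is at baseline (Protocol 9.5.3): "Assessment will be made whether the CGM baseline data meet the criteria of minimum 6 days are recorded". Neither document states a minimum for the treatment weeks. SAP 7.10.4 analyzes the CGM parameters by a one-factor ANOVA on treatment, with no term for recorded time. SAP 10 lists no change on this point.

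**The concern.** Mean glucose and the percentage of time below a threshold do not grow with the number of readings. An episode count does. If a window holds fewer recorded hours, fewer episodes can be counted in it, whatever the subject's hypoglycemia. Change from baseline to Week 4 then mixes a change in hypoglycemia with a change in recording time, and the planned ANOVA cannot separate them.

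The episode rule also refers to plasma glucose, although a CGM records interstitial glucose. In this trial plasma glucose is a separate measurement, made with a YSI analyzer during the clamp, so the rule should name its data source correctly.

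**Working it through.** **1. The plan's own figure.** One reading every 5 minutes gives 24 × 60 / 5 = 288 per complete day, as SAP 7.2.10 states.

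**2. Formulas.** Let λ be the true number of episodes per day and w the days recorded in a window.

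- Expected count under the SAP rule: λ × w.
- Change from baseline with no true change: λ × (w₄ − w_b), or w₄/w_b − 1 as a proportion. λ cancels from the proportion.
- Episodes per recorded day: (λ × w)/w = λ, so the change is 0 for any wear.

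**3. Results.** λ = 1 per day is an assumption and affects only the third column.

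| Baseline days | Week 4 days | Change in weekly count | Percent | Change per recorded day |
|---|---|---|---|---|
| 6 | 6 | 0 | 0 | 0 |
| 7 | 6 | −1 | −14.3% | 0 |
| 6 | 7 | +1 | +16.7% | 0 |
| 7 | 5 (hypothetical) | −2 | −28.6% | 0 |

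**4. Why recorded time can differ between windows.**

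- Baseline: 6 and 7 recorded days both qualify.
- Week 4: Protocol 7.1 has the CGM data retrieved before the repeat induction. Protocol 9.5.7 puts Visit 7 on Day 28±1 with arrival at about 6 to 9 am (Table 6 gives Day 27-28±1). Table 6 shows no new sensor at Visit 7.
- Taking Visit 3 as Day 1, calendar days, and retrieval on arrival on Day 28 (the last is an assumption), Week 4 holds 6 + 6/24 = 6.25 to 6 + 9/24 = 6.375 days. Against 7 baseline days that is −10.7% to −8.9%.
- If study days are instead 24-hour periods from a first dose at 14:00, with retrieval at 08:00 on Day 28 (both times assumed), Days 22 to 28 hold 5.75 days, or −17.9%.
- A Visit 7 on Day 29 would leave the calendar window complete. Protocol 9.5 also calls randomization day zero, although Visit 3 is headed Day 1. On day-zero numbering, a Day 28 visit is SAP Day 29 and the calendar window is again complete.

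**5. Does the merging rule change this?** Simulated 5-minute traces (400; assumed mean 140 mg/dL, SD 45, lag-one autocorrelation 0.98; one random gap per trace) were scored with the SAP rule at 70 mg/dL.

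| Days recorded | Mean weekly count | Episodes per recorded day |
|---|---|---|
| 7 | 19.73 | 2.818 |
| 6 | 16.86 | 2.810 |
| 5 | 14.24 | 2.848 |
| 3.5 | 9.85 | 2.813 |

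The count falls with recorded time (16.86/19.73 − 1 = −14.5% at 6 days), while the rate per recorded day stays level.

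**6. Between arms.** If every arm has 6 Week 4 days and baseline rates are balanced, a true difference in Week 4 counts is multiplied by 6/7. A zero difference stays zero.

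**The case against.** **The count has a window.** A reader might infer that the endpoint has no denominator of any kind. That goes too far: it is derived per day and per week, so it is a rate per calendar window. What is missing is the adjustment when a window is only partly recorded.

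**Bias between arms.** A reader might infer that pump burden or dropout biases the treatment comparison. The documents do not support this. Placebo runs through the same device at matched high and low rates (Protocol 7.1 and 8.4), and all arms share one schedule of CGM retrieval and sensor insertion. A subject who leaves before Week 4 has no Week 4 CGM data, and nothing in the SAP scores that subject as zero; only a partial last week would be undercounted.

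**Size.** Fewer than 6 days cannot enter the baseline, because Protocol 9.5.3 requires a repeat period and then ends participation. No document suggests that 4 or 5 recorded days is typical on treatment.

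**Importance.** A reader might infer that this endpoint speaks most directly to the proposed indication. Protocol 6.1 gives that as prevention of severe hypoglycemia, which is a separate subject-reported item, and SAP 2.1 words the indication differently. SAP 7.10.5 makes all secondary endpoints descriptive. The CGM tables are not marked for the primary endpoint analysis in SAP 12. Proportional time at the same thresholds already accounts for wear and gives a cross-check.

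**Plasma or interstitial.** The section title and 7.2.10.1 make clear that the data come from CGM, so this is a wording fault that a programmer could resolve.

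These objections limit scope and weight. They do not supply the missing adjustment.

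**Conclusion.** The point holds for within-arm change. As written, change from baseline in the episode count partly reflects how long the CGM recorded. The figure tied to the plan's own 6-day criterion is −14% for 6 days against 7, or +17% the other way, with no true change. The Week 4 shortfall of about 9% to 18% depends on clock times and day numbering that the documents do not settle; larger shortfalls are hypothetical. All these figures assume a constant episode rate over the window.

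A shortfall common to all arms distorts the reported change within each arm without creating a treatment difference. Wear that varies between subjects adds noise, with 16 per arm. Bias between arms would need wear to differ by arm, and the documents give no specific reason to expect that. The primary endpoint and its testing hierarchy are untouched. The rule should be corrected because the section already derives the divisor it needs.

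**What to change.** In SAP 7.2.10, define the rate at each threshold as the number of interstitial-glucose episodes below X divided by the CGM time with valid readings in the window. Scale it to 24 hours for the daily version and to 7 days for the weekly version. Replace PG with interstitial glucose in that rule and in the rule that merges consecutive readings.

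The cost is a change to one definition. Recorded CGM time is already derived for proportional time, and no new data, visits or tables are needed. The downside is that rates from windows with very little recorded time are less stable. Reporting recorded time beside the rate, or setting a minimum per window before unblinding, would deal with that.
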